ENDPOINT	
Primary performance endpoints
 
• Improvement of surgical scars at 3 months post-treatment as evaluated by independent blinded reviewer using the General Aesthetic Improvement Scale (GAIS) and Manchester Scar Scale (MSS).• Improvement of surgical scars at 10 months post-treatment as evaluated by independent blinded reviewer using the General Aesthetic Improvement Scale (GAIS) and Manchester Scar Scale (MSS). 
Secondary performance endpoints
 
• Improvement of surgical scars at 1 and 2 months post-treatment as evaluated by independent blinded reviewer using the General Aesthetic Improvement Scale (GAIS) and Manchester Scar Scale (MSS).• Assessment of surgical scars at 3 and 10 months post-treatment as evaluated by independent blinded reviewer using the Patient and Observer Scar Assessment Scale.• Assessment of surgical scars at 3 and 10 months post-treatment as evaluated by the subject using the Patient and Observer Scar Assessment Scale.• Subjects' assessment of satisfaction with the treatment at 3 and 10 months post-treatment. 
Safety endpoints
 
• Subject's assessment of discomfort and pain after treatment as measured by a 10 cm visual analog scale (VAS).• Subjects experiencing a treatment-related adverse event (AE) by 10 months post-treatment.
POPULATION	The study will enroll up to 50 female subjects requesting treatment of surgical scars following breast augmentation or abdominoplasty and up to 25 male and female subjects requesting treatment of surgical scars following face lift surgery.

PHASE	Post-marketing
NUMBER OF SITES	One site
DESCRIPTION OF DEVICE	The Venus Viva™ fractional RF device has been shown in clinical studies to improve various skin conditions related to aging and alter collagen structures such as wrinkles, rhytids and scars. The device utilizes a 160 pin tip to deliver fractional RF energy to the skin.
STUDY DURATION	Approximately fifteen months
PARTICIPANT DURATION	Twelve months

SCHEMATIC OF STUDY DESIGN

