7.3.7 SCHEDULE OF EVENTS TABLE

Procedures	Screening/Baseline (Visit 1, Day -1)	Enrollment/Treatment (Visit 2, Day 0)	Follow-up (Visit 3, Day 0+2 days)	Treatment & Follow-up (Visit 4, Month 1 (± 7 days))	Follow-up (Visit 5, Month 1+2 days)	Treatment & Follow-up (Visit 6, Month 2 (± 7 days))	Follow-up (Visit 7, Month 2+2 days)	Follow-up (Visit 8, Month 3 (± 7 days))	Follow-up (Visit 9, Month 4 (± 7 days))	Follow-up (Visit 10, Month 5 (± 7 days))	Final Study Visit (Visit 11, Month 12 (± 14 days))
Informed consent	X										
Inclusion/exclusion criteria	X	X									
Demographics	X										
Medical history	X										
Physical exam	X										
Vital signs		X	X	X	X	X	X	X	X	X	X
Urine pregnancy test ^a	X										
Test Spot	X										
Photographs		X						X	X	X	X
Administer Treatment		X		X		X					
Discomfort/Pain VAS	X		X		X						
PI immediate & short-term response	X		X		X						
Blinded reviewer GAIS		X						X	X	X	X
Blinded reviewer MSS	X							X	X	X	X
Blinded reviewer POSAS	X									X	X
Subject POSAS	X									X	X
Subject satisfaction questionnaire										X	X
Concomitant medication	X	X	X	X	X	X	X	X	X	X	X
Adverse event evaluation		X	X	X	X	X	X	X	X	X	X

Procedures	Screening/Baseline (Visit 1, Day -1)	Enrollment/Treatment (Visit 2, Day 0)	Follow-up (Visit 3, Day 0+2 days)	Treatment & Follow-up (Visit 4, Month 1 (± 7 days))	Follow-up (Visit 5, Month 1+2 days)	Treatment & Follow-up (Visit 6, Month 2 (± 7 days))	Follow-up (Visit 7, Month 2+2 days)	Follow-up (Visit 8, Month 3 (± 7 days))	Follow-up (Visit 9, Month 4 (± 7 days))	Follow-up (Visit 10, Month 5 (± 7 days))	Final Study Visit (Visit 11, Month 12 (± 14 days))
^a For women of child-bearing potential.											

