10.2 STATISTICAL HYPOTHESES

The null and alternative hypotheses for the study's primary, key secondary and safety endpoints are;

- Primary Performance Endpoint:
 - **Null Hypothesis ($H_0: \mu_d = \mu_{post} - \mu_{pre} = 0$)** – There is no improvement of surgical scars at 3 months post-treatment review compared to baseline.
Alternative Hypothesis ($H_a: \mu_d = \mu_{post} - \mu_{pre} \neq 0$) – There is improvement of surgical scars at 3 months post-treatment review compared to baseline. The improvement of surgical scars will be defined by General Aesthetic Improvement Scale (GAIS) and Manchester Scar Scale (MSS) scores evaluated by independent blinded reviewer. Expected mean improvement difference is not less than one (1) GAIS and MSS score higher than baseline.
 - **Null Hypothesis ($H_0: \mu_d = \mu_{post} - \mu_{pre} = 0$)** – There is no improvement of surgical scars at 10 months post-treatment review compared to baseline.

Alternative Hypothesis ($H_a: \mu_d = \mu_{post} - \mu_{pre} \neq 0$) – There is improvement of surgical scars at 10 months post-treatment review compared to baseline. The improvement of surgical scars will be defined using General Aesthetic Improvement Scale (GAIS) and Manchester Scar Scale (MSS) scores evaluated by independent blinded reviewer. Expected mean improvement difference is not less than one (1) GAIS and MSS score higher than baseline.

- Secondary Performance Endpoint(s):
 - **Null Hypothesis ($H_0: \mu_d = \mu_{post} - \mu_{pre} = 0$)** – There is no improvement of surgical scars at 1 and 2 months post-treatment review compared to baseline.
Alternative Hypothesis ($H_a: \mu_d = \mu_{post} - \mu_{pre} \neq 0$) – There is improvement of surgical scars at 1 and 2 months post-treatment review compared to baseline. The improvement of surgical scars will be defined using General Aesthetic Improvement Scale (GAIS) and Manchester Scar Scale scores evaluated by independent blinded reviewer.
 - **Null Hypothesis ($H_0: \mu_d = \mu_{post} - \mu_{pre} = 0$)** – There is no improvement of surgical scars at 3 and 10 months post-treatment review compared to baseline.
Alternative Hypothesis ($H_a: \mu_d = \mu_{post} - \mu_{pre} \neq 0$) – There is improvement of surgical scars at 3 and 10 months post-treatment review compared to baseline. The improvement of surgical scars will be defined using Patient and Observer Scar Assessment Scale (POSAS) scores evaluated by independent blinded reviewer.

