10.4 DESCRIPTION OF STATISTICAL METHODS

10.4.1 GENERAL APPROACH

All summary tables for quantitative parameters will display mean, standard deviation, median, range (minimum and maximum), percentages as well as number of missing data (if relevant). All summary tables for qualitative parameters will display counts, percentages and number of missing data if relevant. Baseline data are defined as the last measurement performed before the first treatment on Visit 2.

All statistical tests will be two-sided. The level of statistical significance for effectiveness analyses is 5% ($\alpha = 0.05$) for all tests of differences. Where appropriate, Paired t-test and/or Wilcoxon Signed-Ranks Test for Matched Pairs will be used to compare the evaluations at the baseline and post treatment sessions. This test will enable us to accept or reject the null hypotheses. Rejection of null hypotheses will establish that:

- The two-sided 95% confidence interval for the difference between the means excludes zero.
- The two means are statistically significantly different at the 5% level ($P < 0.05$) two-sided.

Upon rejection of null hypotheses, further statistical test tools such as Confidence Interval and/or t-test will be used to determine the performance of Venus Viva™ fractional RF System in the treatment of surgical scars following breast augmentation, abdominoplasty or face lift.

In order to accommodate imbalances of some baseline General Aesthetic Improvement Scale (GAIS) and Manchester Scar Scale (MSS) scores, covariate adjustment analysis may be performed in SAP to estimate adjusted treatment effects for the primary endpoint analysis.

The assumption for the statistical test is that the paired differences of baseline and post treatment data are normally distributed.

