10.4.2 ANALYSIS OF THE PRIMARY PERFORMANCE ENDPOINT(S)

The following will be considered for the analysis primary performance endpoint:

Summary table for differences of baseline, 3-month and 10-month post treatment General Aesthetic Improvement Scale (GAIS) and Manchester Scar Scale (MSS) scores will be displayed as mean difference, standard deviation and standard error. The General Aesthetic Improvement Scale (GAIS) scores is a 5-point scale improvement assessment chart while Manchester Scar Scale (MSS) is two scales whose scores are combined - an overall VAS and seven scar parameters.

Bar, pie charts or graphs indicating scores will also be used to analyse performance, where applicable.

All statistical tests will be two-sided. The level of statistical significance for effectiveness analyses is 5% ($\alpha = 0.05$) for all tests of differences. Where appropriate, Paired t-test and/or Wilcoxon Signed-Ranks Test for Matched Pairs will be used to compare the evaluations of General Aesthetic Improvement Scale (GAIS) scores and Manchester Scar Scale (MSS) scores at 3 and 10 months against baseline. Analysis of Covariance (ANCOVA) may also be used where appropriate.

The Paired t-test and/or Wilcoxon Signed-Ranks Test for Matched Pairs will enable us to accept or reject the null hypotheses. Rejection of null hypotheses will establish that:

- The two-sided 95% confidence interval for the difference between the means excludes zero.
- The two means are statistically significantly different at the 5% level ($P < 0.05$) two-sided.

Upon rejection of null hypotheses, further statistical test tools such as Confidence Interval and/or t-test will be used to test expected primary performance endpoint; that is alternative hypothesis that $H_a \geq 1$. This will be used to determine if the study meets the primary performance endpoint.

General Aesthetic Improvement Scale (GAIS) scores and Manchester Scar Scale (MSS) scores of all subjects who received at least one treatment of Venus Viva™ system for the treatment of surgical scars following breast augmentation, abdominoplasty or face lift and for whom at least one valid post-baseline GAIS and MSS assessment were obtained will be analysed for the primary endpoint. Multiple imputation method or modelling of available data may be used for missing data as appropriate.

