10.4.6 BASELINE DESCRIPTIVE STATISTICS

Subjects baseline scores of all endpoints (GAIS, MSS and POSAS) will be compared using descriptive statistics such as mean score, standard deviation, standard error, range and graphical presentations.

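### GAIS already rates change, yet the plan tests GAIS post minus pre and applies a one-point rule to a baseline value that it never defines

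*Combined protocol and SAP*

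**What the plan says.** The Protocol Summary gives the first primary endpoint as "Improvement of surgical scars at 3 months post-treatment as evaluated by independent blinded reviewer", using GAIS and MSS, with a second at 10 months. Section 10.4.2 describes the instrument: the GAIS "scores is a 5-point scale improvement assessment chart".

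The analysis sections treat GAIS as a level measured before and after treatment:

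- Section 10.2 sets the null as mean post minus mean pre equal to 0, in words "There is no improvement of surgical scars at 3 months post-treatment review compared to baseline", and adds: "Expected mean improvement difference is not less than one (1) GAIS and MSS score higher than baseline".
- Section 10.4.2 compares GAIS and MSS "scores at 3 and 10 months against baseline" by paired t-test and/or Wilcoxon signed-rank test. After rejection, it tests whether the difference is at least 1 to decide whether the primary endpoint is met.
- Section 10.4.1 defines baseline as the last measurement before the first treatment at Visit 2, and allows covariate adjustment: "In order to accommodate imbalances of some baseline General Aesthetic Improvement Scale (GAIS" and MSS are the scores named.
- Section 10.4.6 states: "Subjects baseline scores of all endpoints (GAIS, MSS and POSAS) will be compared using descriptive statistics".
- Section 10.5 sizes each cohort on a GAIS post-minus-pre difference of 1.0 with SD 1.0.

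The Protocol Summary also says that outcomes will be compared with the untreated side. That comparison appears in none of the hypotheses.

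**The concern.** A rating of improvement has its reference built in: the scar as it was before treatment. Taken literally, a baseline GAIS asks the reviewer how far a scar has improved before anything has been done to it. The documents do not say what such an entry would mean or what number it would carry.

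This bears on the primary conclusion, because the estimated difference, its p-value and the at-least-1 criterion all depend on the number subtracted. If the reference value is settled after the ratings are in, a coding convention could decide whether the GAIS part of the primary endpoint is met.

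**Working it through.** **What post minus pre becomes.** Let Y be a follow-up GAIS rating and r the baseline entry. Before treatment there is nothing to rate, so the only entry with a natural meaning is the no-change category, the same for everyone. Then:

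- mean difference = mean(Y) − r
- SD of the difference = SD(Y), since r does not vary
- the paired test is a one-sample test of Y against r
- a constant baseline covariate is collinear with the intercept, so the Section 10.4.1 adjustment for baseline GAIS drops out.

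**Is r fixed by the documents?** Section 10.5 gives only a GAIS range of 4. That fits codes 1 to 5, 0 to 4, or −2 to +2, and says nothing about where no-change sits. That higher is better is implied only by the one-point expectation in Section 10.2.

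**Sensitivity to r (illustration).** With n = 11 and SD = 1, the test statistic is (mean(Y) − r) × √11 = 3.32 × (mean(Y) − r). A mean one category above r gives 3.32, above the 1.96 printed in Section 10.5. If r is placed one category higher, the same ratings give a difference of 0 and a statistic of 0. The at-least-1 rule changes from met to not met in the same way.

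**The plan's sample size.** Inputs from Section 10.5: two-sided α 0.05, power 0.90, difference 1.0, SD 1.0 (range 4 ÷ 4).

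- n = (SD × (z₀.₉₇₅ + z₀.₉₀) / difference)² = (1 × (1.9600 + 1.2816) / 1)² = 10.51, rounded to 11. This reproduces the plan.
- The 0.84 printed beside 90% power would give (1.96 + 0.84)² = 7.84, so it was not the value used.
- 11 × 1.3 = 14.3, rounded to 15, as stated.
- An exact t calculation needs 13; 11 subjects give 84.8% power by t and 91.3% by the normal approximation.

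The SD is one GAIS range divided by 4. In effect the calculation treats a single rating as the change score, so 11 holds for the one-sample reading.

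**Treated minus untreated.** Assume a between-side difference of 1, SD 1 on each side and within-subject correlation ρ; the documents give none of these for this contrast. The SD of the difference is √(2(1 − ρ)), so n = 10.507 × 2(1 − ρ). Power at 11, by the normal approximation, is Φ(√11 / SD − 1.96).

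| ρ | SD of difference | n (normal) | n (exact t) | Power at 11, normal / t |
|---|---|---|---|---|
| 0 | 1.414 | 21.01 → 22 | 24 | 65% / 56% |
| 0.25 | 1.225 | 15.76 → 16 | 18 | 77% / 69% |
| 0.5 | 1.000 | 10.51 → 11 | 13 | 91% / 85% |
| 0.75 | 0.707 | 5.25 → 6 | 8 | 99.7% / 98.8% |

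**Enrolment ceiling.** Section 10.5 allows up to 25 face lift subjects and 50 for the other two cohorts. If these are filled and the 50 split evenly (assumed), each cohort keeps 25 × 0.7 = 17.5, so about 17 evaluable after 30% loss. By the normal approximation that covers 16 but not 22.

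**The case against.** The best defence is that the plan can be run as it stands. Enter no-change for everyone at baseline, and post minus pre is a valid one-sample t or signed-rank test, with the sample size intact. That is right. It leaves only the reference value, codes and anchors to be stated, and it makes the adjustment for baseline GAIS empty rather than harmful; Section 10.4.1 in any case makes adjustment optional.

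Several stronger readings are tempting and do not hold:

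- *The GAIS test is undefined.* It is mis-specified, with its reference unstated, but it can be computed.
- *GAIS is the lead primary endpoint.* The Protocol Summary and Sections 4.2.1 and 10.2 name GAIS and MSS together without ranking them. GAIS alone drives the sample size, and nothing more.
- *Success is automatic.* With codes 1 to 5 and a baseline of 0, every subject would gain at least 1. But 0 lies off that scale, and nothing in the documents suggests such an entry.
- *The schedule proves a baseline rating.* In Section 7.3.7 the row "Blinded reviewer GAIS" is marked at Visit 2, but nearby rows look displaced: the pain VAS falls at Visits 1, 3 and 5, although the text puts it at the treatment visits. The GAIS marks also match those for photographs. Sections 10.4.1 and 10.4.6 carry this point without the table.
- *The trial needs 43 per cohort.* Treating the outcome as a difference of two free GAIS scores gives range 8, SD 2 and (2 × 3.2415)² = 42.03, rounded to 43. With a constant baseline the SD is that of one rating, so this does not follow.

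A fair objection to the remedy is that treated minus untreated is a different estimand and is not strictly needed to repair the scale. It is, however, the comparison that the Protocol Summary promises, and it uses photographs that Section 7.3.2 already requires.

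**Conclusion.** The point holds for GAIS only. The plan describes an improvement rating and analyses it as a before-and-after level, with a baseline of no stated meaning and a one-point rule that shifts one for one with that baseline. That GAIS carries its own baseline is a reading of the plan's description and of its improvement endpoint; the documents give no anchors that would settle it further. MSS and POSAS are not affected.

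The sizing damage is limited. The 11 evaluable per cohort stand for a one-sample test with mean 1 and SD 1. For treated minus untreated, the requirement runs from 6 to 22 by the normal approximation as ρ falls from 0.75 to 0, given an assumed difference of 1 and SD 1 per side. A smaller true difference, for instance because the untreated side also improves, would raise it. The analysis definition must be corrected before any ratings are seen.

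**What to change.** 1. Delete baseline GAIS from Sections 10.4.1 and 10.4.6, and from Section 7.3.7 if the Visit 2 mark is a rating, together with the covariate adjustment for it.
2. State the five GAIS anchors, their numeric codes and direction, and the no-change value.
3. Have the blinded reviewer rate each side's follow-up photographs against that side's own baseline photographs.
4. Rewrite the GAIS hypotheses in Section 10.2 and the analysis in Section 10.4.2: the primary GAIS analysis is the within-subject treated-minus-untreated rating at 3 and at 10 months, tested against 0 by signed-rank or paired t-test, with the choice named in advance.
5. Report the treated side against the no-change value as supportive, with the at-least-1 rule defined against that value.
6. Keep post minus pre for MSS and POSAS.

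Cost: mainly wording, with two further items. Sections 7.3.3 and 7.3.4 mention follow-up photographs of the treated area only, and must be aligned with Section 7.3.2, which requires both sides. Section 10.5 must restate its basis (between-side difference, SD, assumed correlation) and the resulting power. Restating power, rather than raising enrolment, is the proportionate step. No extra visit is needed, and the baseline rating is dropped.

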10.5 SAMPLE SIZE

One of the primary performance endpoints outcome measures was used to calculate the study sample size.

Sample size calculation using the subject's improvement of surgical scars at 3 months post-treatment as evaluated by independent blinded reviewer using the General Aesthetic Improvement Scale (GAIS);

- Null and alternate hypotheses:
 - **Null Hypothesis ($H_0: \mu_d = \mu_{post} - \mu_{pre} = 0$)** – There is no improvement of surgical scars at 3 months post-treatment review compared to baseline.
 - **Alternative Hypothesis ($H_a: \mu_d = \mu_{post} - \mu_{pre} \neq 0$)** – There is improvement of surgical scars at 3 months post-treatment review compared to baseline. The improvement of surgical scars will be defined by General Aesthetic Improvement Scale (GAIS) scores evaluated by independent blinded reviewer. Expected mean improvement difference is not less than one (1) GAIS score higher than baseline.
- In view of the nature of this study in regard to treatment period of 3 months and up to 10 months follow-up, we make provision for 30% study drop out, withdrawal or loss to follow-up.
- Due to the natures of 3 types of surgical scars that will be treated in this clinical study, the study will be viewed as 3 groups of cohort studies;
 - breast augmentation cohort group
 - abdominoplasty cohort group
 - face lift cohort groupThe study's sample size calculation below is number of subjects required for each group the makes up the study
- 2-Tailed Sample Size calculation formula for Matched Samples was used in the table below:

(1- β), Power	0.9
α , Level of Significance	0.05
μ_d , mean difference; this is the expected improvement (difference) to treatment assessed by GAIS scores under H_a	1.0
σ_d , Standard Deviation of the difference scores (GAIS range $\div 4$) = [4 \div 4]	1.0
ES, Effect Size $[(\mu_d/\sigma_d)]$	1.0
$Z_{1-\alpha/2}$	1.96
$Z_{1-\beta}$, (for 90%)	0.84
Estimated Sample Size	10.51 \approx 11
Estimated Sample Size + 30% drop out	14.30 \approx 15

Conclusion: The estimated sample size for each cohort group obtained from the primary performance endpoint outcome measure calculation plus 30% drop out provision that will be used for this study is 15.

The study will enroll up to 50 female subjects requesting treatment of surgical scars following breast augmentation or abdominoplasty and up to 25 male and female subjects requesting treatment of surgical scars following face lift surgery.

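### The 90% power belongs to a normal-quantile formula, not to either permitted primary test, and the plan does not say which of the two tests decides

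*Combined protocol and SAP*

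**What the plan says.** **Test.** Section 10.4.2 (Analysis of the Primary Performance Endpoint(s)) states: "Where appropriate, Paired t-test and/or Wilcoxon Signed-Ranks Test for Matched Pairs will be used to compare the evaluations of General Aesthetic Improvement Scale" and MSS scores at 3 and 10 months with baseline, two-sided at 5%. It adds ANCOVA as a further possibility. Neither 10.4.1 nor 10.4.2 says which test governs, how a signed-rank p-value is to be computed, or how zeros and ties are handled.

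**Assumption.** Section 10.4.1 (General Approach) says: "The assumption for the statistical test is that the paired differences of baseline and post treatment data are normally distributed".

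**Consequence of rejecting.** Section 10.4.2 says that rejection by either test shows this: "The two-sided 95% confidence interval for the difference between the means excludes zero". Rejection then opens a second step, against a mean improvement of at least 1, which decides whether the primary endpoint is met.

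**Sample size.** Section 10.5 states: "2-Tailed Sample Size calculation formula for Matched Samples was used in the table below". The inputs are a mean difference of 1.0, an SD of 1.0, two-sided alpha 0.05 and power 0.9. The results are 10.51, rounded to 11, and 14.30 with 30% dropout, rounded to 15, for each of three cohorts. The effect is described as follows: "Expected mean improvement difference is not less than one (1) GAIS score higher than baseline".

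**Scale.** Section 10.4.2 says of GAIS that its "scores is a 5-point scale improvement assessment chart".

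**The concern.** The hypotheses in 10.2, the sample size in 10.5 and the second step in 10.4.2 all concern a mean. The Wilcoxon signed-rank test is not a test of a mean, yet it may decide the primary null hypothesis alone or beside the t-test. Differences on a 5-point score are integers with many ties and zeros, so at 10 or 11 subjects the two tests can reach different decisions on the same data. Section 10.6.2 says that the biostatistician is not blinded, so an open choice can be made by someone who has seen the results.

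Two things are at stake. The 90% power that justifies the size may not belong to the test that is run. And the step that opens the assessment against 1 may turn on which permitted test is reported.

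**Working it through.** **1. The plan's figure.** With mean 1.0 and SD 1.0, n = ((z for alpha + z for power) × SD / mean)² = (1.96 + 1.2816)² = 10.51, rounded up to 11. This matches the plan. The z of 0.84 printed in the table would give (1.96 + 0.84)² = 7.84, so it was not the value used. Dropout: 11 × 1.3 = 14.3, rounded up to 15. After 30% loss, 15 × 0.7 = 10.5 remain, that is 10 or 11 evaluable per cohort.

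**2. Paired t-test, normal differences.** Power from the noncentral t with n − 1 degrees of freedom and noncentrality √n × 1.0/1.0:

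- n = 10: 80.3%
- n = 11: 84.8%
- n = 12: 88.3%
- n = 13: 91.1%
- n = 15: 94.9%

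At n = 11 the shortfall is 90 − 84.8 = 5.2 points. It comes from using normal instead of t quantiles and has nothing to do with the Wilcoxon option.

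**3. Integer differences.** The documents give no distribution, so the shapes below are assumptions. Each has mean 1 and variance 1:

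- A: −1, 0, 1, 2 with probabilities 0.1, 0.2, 0.3, 0.4 (mean −0.1 + 0.3 + 0.8 = 1; mean square 0.1 + 0.3 + 1.6 = 2).
- B: −1 to 3, symmetric binomial (1, 4, 6, 4, 1 sixteenths).
- C: 0, 1, 2, 3 with probabilities 0.4, 0.3, 0.2, 0.1 (mean 0.3 + 0.4 + 0.3 = 1; mean square 0.3 + 0.8 + 0.9 = 2).

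Each cell is 20,000 simulated trials, two-sided 0.05. The signed-rank test drops zeros and uses midranks. Exact means the conditional permutation p-value. Approximate means the tie-corrected normal p-value without continuity correction. Disagreement is with the t-test.

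| Shape | n | t-test | Exact signed-rank | Disagree | Approx. signed-rank | Disagree |
|---|---|---|---|---|---|---|
| A | 10 | 75.5% | 63.7% | 12.1% | 75.0% | 2.5% |
| B | 10 | 79.4% | 65.0% | 14.4% | 77.6% | 2.0% |
| C | 10 | 85.3% | 63.1% | 22.2% | 83.9% | 1.4% |
| A | 11 | 80.5% | 72.6% | 8.6% | 80.6% | 1.8% |
| B | 11 | 84.1% | 73.3% | 10.9% | 82.9% | 1.6% |
| C | 11 | 91.5% | 75.2% | 16.3% | 90.6% | 1.0% |
| A | 15 | 92.9% | 91.9% | 1.7% | 93.5% | 0.7% |
| B | 15 | 95.5% | 92.8% | 2.8% | 95.4% | 0.3% |
| C | 15 | 99.3% | 96.7% | 2.6% | 99.2% | 0.1% |

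A separate run of 4,000 trials per cell, with a rounded normal as the symmetric shape, gave 63-65% at n = 10 and 72-77% at n = 11 for the exact test, with disagreement of 9-23%. A wider set of shapes gave 63-71% and 71-81%. With continuity correction, the approximate test on A to C has 68-71% and 76-79%. At n = 17 (25 enrolled less 30% is 17.5) the exact test has 95-99% on A to C, with about 1% disagreement.

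**4. The confidence-interval statement.** Rejection by the two-sided t-test and exclusion of zero by the t-based 95% CI are the same event, so the statement is true of the t-test. The signed-rank test has no such link to the mean. In the simulations it rejected alone in at most about 0.4% of trials, so this is an error of logic more than of frequency. Nearly all disagreement ran the other way: the t-test rejected and the exact signed-rank test did not.

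**The case against.** **A reader might infer that the Wilcoxon test as such has only about 63-77% power here and often contradicts the t-test.** The documents do not support that. They name no version of the test, and on the same data the uncorrected approximation is within about 2 points of the t-test. The low figures belong to the exact version, under assumed shapes, at 10-11 evaluable.

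**A reader might also put the whole shortfall from 90% on the Wilcoxon option.** That is wrong too, because the t-test itself falls short on normal data.

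**Is 10-11 too pessimistic?** Section 10.5 allows up to 25 face-lift and up to 50 body-scar subjects. Section 10.3 keeps any treated subject with one valid post-baseline evaluation, and 10.4.2 permits imputation. Section 10.4.2 also describes the analysis over all three scar types without specifying a test per cohort. Pooled, 45 × 0.7 = 31.5 evaluable would make the gap negligible. These points limit the size of the problem. But the enrolment figures are ceilings, the 50 is shared by two cohorts with no stated split, and 10.5 attaches its 90% to each cohort at 15 enrolled. That is the claim tested here.

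**Is a rank test defensible?** Yes, for an ordinal score; 10.4.3 itself calls these tools ordinal. But the plan's hypotheses, sample size and second step are all about a mean, and 10.4.1 assumes normal differences. The t-test is the option that fits the rest of the plan.

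**Conclusion.** The point holds in a limited form. The sample-size arithmetic reproduces, but it is not the power of either permitted test. At the plan's own effect and SD the paired t-test has 84.8% at 11 evaluable and 80.3% at 10. The signed-rank test at those sizes ranges from about 63-65% to 75-84% (n = 10) and from about 72-77% to 81-91% (n = 11), depending on a p-value method that the plan does not state. Disagreement with the t-test runs from 1-3% (uncorrected approximation) to about 8-23% (exact).

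The t-test figures assume normal differences. The signed-rank figures rest on assumed integer shapes. Both rest on 10-11 evaluable per cohort, and by 15-17 the difference between tests is small. Two defects need none of these assumptions: no rule says which test decides, and the confidence-interval statement is false for a Wilcoxon rejection. The plan should be changed, though nothing here shows that the study cannot succeed.

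**What to change.** - **10.4.1 and 10.4.2:** name the paired t-test, with its 95% CI, as the single primary test. It matches the hypotheses in 10.2, the sample size and the criterion of at least 1.
- **Wilcoxon:** keep it as a sensitivity analysis that cannot change the primary conclusion. State whether its p-value is exact or approximate, whether a continuity correction applies, and how zeros and ties are treated.
- **Confidence-interval statement:** limit it to the t-test.
- **10.5:** name the paired t-test as the test to which the power refers. Replace 90% with about 85% at 11 and 80% at 10 evaluable per cohort, and correct the printed z of 0.84.

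These are wording changes with no extra subjects, visits or procedures. The cost is a less favourable stated power, and a primary inference that rests on the mean of an ordinal score, as the plan's hypotheses already do. If the sponsor prefers to keep 90% for the t-test, step 2 of the working shows that 13 evaluable per cohort are needed: 13 / 0.7 = 18.6, so 19 enrolled. That fits the ceilings (2 × 19 = 38 of 50, and 19 of 25) if the body-scar places are split between the two cohorts.
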